Please choose which level of review best fits your research. This is an investigator's assessment of review and does not preclude the IRB from alternate determinations. In cases where the investigator and the IRB's determination of review conflict, the IRB's determination will be considered the official determination.

Note: "Expedited" review does not refer to the timeliness of the review of your protocol, but specific categories of research defined by OHRP. If you would like help determining which type of review best fits your research study, please contact the IRB staff in the Office of Research Support & Compliance: <https://research.utexas.edu/ors/human-subjects/get-help/>

Click on the appropriate check box (or double click and type an "X" if using Google Docs):

- Full Committee – Greater than Minimal Risk Research
- Single Reviewer – Minimal Risk Research (expedited)

1a. Notification of UT IRB Fees

Be aware that the UT IRB may charge fees for certain types of reviews. If your project qualifies for either of the project types listed below, check the appropriate box and review our website for more information about IRB fees that may apply. Please reach out to [contact] if you have questions.

- Industry-sponsored Clinical Trial
- Federally-Funded multisite study for which UT IRB is serving as the single IRB of record (for guidance, see our website for Single IRB Reliance)

2. External Time Limitation

Generally, the IRB will review applications in the order in which they are received. When possible, the IRB can assign higher priority to research with externally-imposed urgency that is beyond the control of the researcher (example: grant deadlines, research responding to a sudden or emerging event, etc.).

Completing this section provides the IRB with information but does not guarantee priority review is possible or that a requested deadline can be met. Researchers are encouraged to communicate with the IRB as soon as possible when there is an urgent situation (ideally before submitting the IRB application), and we will do our best to accommodate requests, as possible: <https://research.utexas.edu/ors/human-subjects/get-help/>

Are you requesting the IRB consider priority review due to an externally-imposed deadline or time limitation affecting this submission?

- No
- Yes → *If yes, briefly describe the urgency or deadline below, including the reason for it:*

The sponsor has requested expedited review in order to ensure funds are available for this project.

3. Is the research taking place at or using data from any of the following:

Knowing when UT's external clinical partners are involved helps inform IRB review and reporting.

- None of these
- Health Discovery Labs
- Central Health

- CommUnity Care
- Ascension locations → *Submit a request to the [Seton Site Approval Tool \(SAT\)](#) and upload the confirmation email that states the request has been submitted in UTRMS under "Other Documents." Please note, we do NOT need the final approval letter (you will not receive SAT approval until after IRB approval is granted). If you encounter issues or have questions about SAT, please reach out to [contact].*

4. Research Hypotheses

Please describe the research aims and hypotheses in the box below. Note: Procedures will be explained in a separate section below.

Aim 1: To assess the efficacy of lumateperone 42 mg administered once daily compared with placebo in the treatment of patients with Major Depressive Disorder and early life abuse, as measured by change from baseline to end of Week 6 in MADRS total score.

Aim 2: To assess neurocircuitry encoding of threat and reward learning as predictors of lumateperone response and as mechanisms of treatment action, and assess the change from pre-dose to post-dose of task-evoked brain activation.

Aim 3: MADRS response rate (proportion of subjects with an improvement $\geq 50\%$ in the Baseline MADRS total score) at Week 6 of Lumateperone as compared to Placebo.

Aim 4: MADRS remission rate (proportion of subjects with a MADRS total score ≤ 10) at Week 6 of Lumateperone as compared to Placebo.

Aim 5: To assess the efficacy of lumateperone 42 mg administered once daily compared with placebo in the treatment of patients with Major depressive Disorder and early life abuse, as measured by change from baseline to end of Week 6 in Clinical Global Impression-Severity (CGI-S) score.

5. Study Background

Provide the rationale and the scientific or scholarly background for the proposed activity, based on existing literature (or clinical knowledge). Describe the gaps in current knowledge that the project is intended to address.

Early life trauma is widely documented as a robust risk factor for development of major depressive disorder (MDD), in addition to many other mental health disorders^{1,2}. Further, comorbid history of early life trauma among those with MDD predicts worse response to first-line pharmacotherapy for MDD². Among the different types of early life traumas, physical and sexual assault tend to be associated with particularly worse outcomes in adulthood³. As such, there is a clear need to develop adjunctive therapies for those with MDD and histories of early life abuse in order to mitigate the typical poor clinical response seen in this population.

An emerging computational neuroscience literature has demonstrated altered neurocircuitry encoding of threat and reward learning as a key mechanism linking early life abuse to worse mental health outcomes in adulthood. This emerging computational literature complements and extends the well-established link between MDD and poor reward learning and decreased reward sensitivity⁴⁻⁶. Indeed, in a prior study we demonstrated that decreased prospective reward representations in the striatum mediated poorer reward learning and depression symptoms among individuals with histories of early life physical or sexual assault⁷. We've also demonstrated decreased encoding of reward prediction errors among women exposed to physical or sexual assault in the striatum and anterior insula^{8,9}, and decreased social reward prediction error encoding among adolescent girls who experienced physical or sexual assault. Similarly, recent work demonstrated altered integration of threat and reward learning (i.e., approach-avoidance conflict) in depression^{10,11}, potentially mediated by altered encoding of reward in the striatum. These findings are in line with our prior computational work investigating neurocircuitry mechanisms of approach-avoidance conflict demonstrating that biased prospective representations of reward vs threat in

the salience network mediates decisions to approach reward vs avoid threat¹² and that individuals with assault histories demonstrate altered approach-avoidance conflict learning^{13,14}. Overall, the emerging literature clearly points to altered computational encoding of threat and reward learning as a mechanism underlying development of MDD among those with histories of early life assault.

The neurocircuitry implicated in altered threat and reward learning as mechanisms of risk for MDD includes the salience network (dorsal anterior cingulate cortex and anterior insula) and striatum. Notably, this neurocircuitry overlaps with dopaminergic and serotonergic pathways targeted by atypical antipsychotic medications^{15,16}. As such, altered neurocircuitry encoding of threat and reward learning could potentially be predictive of clinical outcomes for adjunctive therapies that target these pathways, such as lumateperone. There are two main routes by which these pathways could have clinically predictive significance. First, individual differences in neurocircuitry encoding of threat and reward learning could operate as markers of who would vs would not benefit from lumateperone adjunctive therapy. Second, pre- to post-treatment changes in neurocircuitry encoding of reward and threat learning could operate as a mechanism of symptom reduction (e.g., lumateperone induced improvements in reward and threat neurocircuitry encoding mediate reductions in depression symptoms). These possibilities are not mutually exclusive, and both would have considerable clinical significance for enabling precision medicine approaches to the treatment of MDD among early life trauma populations.

6. Design and Methodology

Provide a brief description of the overall study design or data collection methodologies. Details regarding protocol specific research procedures will be discussed in the next section below.

This is a single site investigator initiated randomized, double-blind, placebo controlled, fixed-dose study in patients with a primary diagnosis of MDD, a history of early life abuse, and who have an inadequate response to on-going SSRI treatment. The study will enroll a total of 50 participants (n=50) with 25 randomized to treatment and 25 to a placebo, and will be conducted in 3 phases:

Screening Period - After signing the ICF, an identification number will be assigned to the subject. Prior to randomization, all subjects will enter a 2 week-day screening period (Screening) to determine eligibility. Eligible subjects must meet the Diagnostic and Statistical Manual of Mental Disorders, Fifth Edition (DSM-5) criteria for MDD without psychotic features, based on the DIAMOND (Diagnostic Interview for Anxiety, Mood, and Other Neuropsychiatric Disorders), with a current major depressive episode of at least 8 weeks in duration. They must have had an inadequate response (<50% symptom reduction) to an adequate trial of at least 1 antidepressant therapy (ADT) (as determined by administering the Massachusetts General Hospital Antidepressant Treatment History Questionnaire [ATRQ]) in their current Major Depressive Episode (MDE). During Screening Period (2 weeks) patient eligibility will be assessed and a Pre-dose fMRI performed.

Double-blind Treatment Period - Double-blind Treatment Period (6 weeks) during which all eligible patients will be randomized to receive lumateperone 42 mg or placebo in 1:1 ratio. At Baseline (Visit 2), patients who continue to meet all eligibility criteria will be randomized to either lumateperone or placebo.

Safety Follow-up Period in which all patients will return to the clinic for a safety follow-up visit approximately one week after the last dose of study treatment. All patients will complete a post dose MRI 1 week after the 6-week study period is completed.

- During the Pre-Dose and Post-dose MRI, Participants will undergo standard structural imaging as well as functional imaging during computational threat and reward learning tasks. Computational neuroimaging approaches will characterize neurocircuitry encoding of anticipating and delivery of threat and reward outcomes, enabling testing of predictors of lumateperone clinical response and mechanism of treatment action.

- Patients who discontinue study drug prior to Week 6 but agree to continue participation in the Double-blind Treatment Period (DBTP) should be seen at all subsequent protocol-defined visits up to week 6 and should also return for the SFU Visit for post dose MRI. Study drug will no longer be dispensed for these patients and the clinical management of these patients will be at the discretion of the Investigator.
- Patients who discontinue study drug prior to Week 6 and do not agree to continue participation in the DBTP should be seen for an early termination (ET) Visit as soon as possible and should also return for the SFU Visit 1 week after the ET Visit. Study drug will no longer be dispensed for these patients and the clinical management of these patients will be at the discretion of the Investigator;

Safety Follow-up Period (1 week) during which all patients will return to the clinic for a safety follow-up (SFU) Visit approximately one week after the end of DBTP, or ET Visit if the patient does not complete the DBTP.

7. Study Procedure Description

Provide a step-by-step narrative of what enrolled participants will be asked to do or allow, and/or how data/specimens will be collected and used, such that someone else could replicate the procedures based on this description.

Recruitment and consent procedures will be covered in later sections. The description below should cover all procedures involving enrolled subjects or participants (or their data/specimens) from start to finish, in sequential order. Include details of all the following, as applicable:

- Research measures/tests/data collection tools that will be used. **Upload copies of all surveys, interview guides, assessments, questionnaires, and any other data collection tools to UTRMS-IRB in the “Other Attachments” section.**
- Research interventions and activities, including all stimuli/tasks/instructions that participants will see, hear, or experience as part of their participation. **Upload copies of all intervention materials (including videos, audio files, handouts, photos, scripts, etc.) to UTRMS-IRB in the “Other Attachments” section.**
- Biospecimens that will be collected as part of the research procedures, including the type of specimen, method of collection, schedule/frequency of collection.
- Secondary data or specimens that will be obtained, how they are collected and used, from what source(s).
- Total duration of all research activities (i.e. expected time commitment of participants).

[figure not shown]
Note: if this is a Multi-Site or Collaborative Study include the following:

- *This is a “Multi-Site Study that involves more than one site performing ALL aspects of the research procedures as outlined above.” OR “This is a Collaborative Study that involves UT Austin researchers working with external researchers who are engaged in performing the following study activities (list activities).”*
- *For assistance with Multi-Site/Collaborative research, review [UT Guidance: Submitting Studies Relying on UT IRB](#), download HRP-UT932 Request to Rely Assessment Form from the [UTRMS-IRB Library](#) and email [contact].*

This is a single site, randomized, double-blind, placebo-controlled study to evaluate the efficacy of lumateperone as an adjunctive treatment of patients with MDD and a history of early childhood abuse. During the study subjects currently receiving approved dosing regimen of ADT, who experience an inadequate therapeutic response according to MADRS score at Baseline, will be randomized in a 1:1 ratio to Lumateperone 42mg or placebo, and receive treatment for 6 weeks. The primary efficacy analysis will be based on the week 6 assessment of the primary and secondary efficacy endpoints. The overall duration of the study, including Screening and intervention period, will be approximately 9 weeks per subject: a 2-week screening period, 6 weeks of double-blind treatment, and a 1-week safety follow-up visit.

The study design is presented in Figure 1.

Figure 1.

The study will be conducted as follows:

- Screening Period (2 weeks):
- A 2-week Screening Period during which patient eligibility will be assessed. After obtaining written informed consent, diagnostic interviews and physical examinations will be conducted, vital signs and ECGs will be assessed, and blood and urine samples will be collected for laboratory assessments. With the exception of stable, allowed concomitant medications, patients must discontinue prohibited psychotropic drugs during the Screening Period. The following rating scales will be administered.

Clinician Rater: CAPS-5, MADRS, DIAMOND, SCID-5 Borderline Personality module, CGI-S, MGH-ATRQ, CSSRS

PROS, GAD-7, QIDS-SR-16, EQ 5D-5L, CTQ, GASS, PCL-5, NWS, MCI

Once deemed eligible, the subject will also be offered to enroll in the optional EMA wellness app to be completed 3X daily from screening visit to the end of study visit

- Double-blind Treatment Period (DBTP, 6 weeks):
 - At Baseline (Visit 2), patients who continue to meet all eligibility criteria will be randomized to 1 of 2 treatment arms, lumateperone 42 mg or matching placebo, and will enter the 6-week DBTP. Patients will be administered the first dose of study drug in the evening of the Baseline Visit (Visit 2/Day 1). A single dose will be taken each evening, with or without food, for the duration of the 6-week DBTP.
 - MRI assessments will be completed at baseline Pre- dose and post dose at 1-week safety follow up visit.

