7.2.4 Safety Follow up (Visit 8: Week 7)

1. Record AEs as reported by patient or observed by Investigator
2. Review concomitant medications
3. Study drug compliance check, return unused Meds
4. Vital signs (BP, pulse rate, body temperature, respiratory rate) and weight
5. fMRI Assessments.

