11.2 Statistical And Analytic Plan

The primary efficacy endpoint is the change from baseline to end of Week 6(EOT) in MADRS total score. Based on the primary hypothetical estimand strategy which assumes patients are on study drug up to the primary time point (end of Week 6), MADRS assessments collected off-treatment (ie, efficacy assessment performed more than 3 days after last dose of study drug) and/or after starting new treatment for MDD will be set to missing (except those collected for patients discontinued due to and will not be included in the primary analysis). The missing data in patients who discontinued due to lack of efficacy (LOE) or due to taking non-study treatment for MDD will be assumed missing-not-at-random. The missing data in patients who discontinued due to other reasons will be assumed as missing- at-random. Missing data will be imputed accordingly to recent recommendations using the ‘mice’ package in R.^{25,26}

The primary analysis will use a mixed-effects model for repeated measures (MMRM) to analyze the change from baseline to end of Week 6 in MADRS total score. Similar MMRM models will be used for secondary endpoints. An additional analysis will examine slopes of MADRS scores over the 6 week period, testing the hypothesis that the active drug group will have a steeper slope of MADRS over the 6 week period. Additional models will test for non-linear patterns of change as well. Similar analyses will be conducted on secondary outcomes (e.g. CGI, PTSD

symptom severity, etc.).

For imaging data, following standard preprocessing, beta coefficients of voxelwise brain activity will be defined using standard general linear models. These coefficients will be used in multivariate pattern analysis (MVPA) to build classifiers, using support vector machines (SVM), of reward and threat using leave-one-out cross-validation and quantify reward and threat anticipation during the task. MVPA classifier output will be analyzed using mixed effects models. Threat and reward anticipation as predictors of treatment outcome will be analyzed by including these variables as a predictor in the MMRM described above. Threat and reward anticipation as targets of treatment will be analyzed in mixed effects model with post-treatment classifier output as the dependent measure and including predictors of drug group and including pre-treatment classifier output as a covariate.

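### The only post-treatment fMRI is scheduled about a week after the last dose, so the pre-to-post and mechanism part of Aim 2 compares the arms after drug has stopped

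*Protocol*

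**What the plan says.** Aim 2 (Protocol, item 4) has two parts. Threat and reward encoding is to be studied as a predictor of response. It is also to be studied as a mechanism of treatment action, and the trial is to "assess the change from pre-dose to post-dose of task-evoked brain activation". Item 5 explains the second part: change in encoding brought about by the drug might carry the reduction in symptoms.

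On timing of the second scan:

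- Item 6 describes a "safety follow-up visit approximately one week after the last dose of study treatment" and then states: "All patients will complete a post dose MRI 1 week after the 6-week study period is completed".
- Item 7, under the double-blind period: "MRI assessments will be completed at baseline Pre- dose and post dose at 1-week safety follow up visit".
- Section 7.2.4 (Visit 8, Week 7) lists "fMRI Assessments". Section 4.2.3 lists no scan at Visits 3 to 7, and Table 1 marks fMRI only at Visits 2 and 8.
- Patients who stop drug early but remain in the study "should also return for the SFU Visit for post dose MRI" (item 6).

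Section 11.2 models the post-treatment classifier output on drug group, adjusting for the pre-treatment output. It sets no limit on days since the last dose. For the primary MADRS analysis, the same section treats an "efficacy assessment performed more than 3 days after last dose of study drug" as off-treatment and in general sets it to missing.

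**The concern.** The question asked is how the drug changes threat and reward encoding, and whether that change accounts for improvement. The only image that could answer it is taken after dosing has ended. No analysis can repair this, because no on-drug image would exist.

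An arm difference at that visit mixes three things: change that outlasts treatment, an effect of stopping, and whatever drug effect remains. If there is no difference, an absent effect cannot be told from one that has washed out.

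The order of measurement adds a second difficulty. The main outcome is MADRS at Visit 7 (Section 11.3). The proposed mediator is measured after it, with the end of dosing in between.

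**Working it through.** This is a timeline check. The protocol gives no half-life and no duration of neural effect after stopping, so no residual effect is calculated.

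**Inputs.** Screening 2 weeks, treatment 6 weeks, follow-up 1 week (item 7). Follow-up visit about one week after last dose (item 6). Visit window ±2 days (Table 1, assumed to apply to Visit 8). Dispensing at Baseline (Week 1) and weekly until Week 5 (Section 3.1). Baseline = Week 1, Visit 7 = Week 6, Visit 8 = Week 7 (Table 1). Off-treatment limit of 3 days for efficacy assessments (Section 11.2).

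**1. The plan's own figure.** 2 + 6 + 1 = 9 weeks, which matches the stated duration of approximately 9 weeks per subject.

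**2. Completers, as the text reads.** Days from last dose to scan: 7 nominal, 7 − 2 = 5 to 7 + 2 = 9 with the window. All exceed 3.

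**3. Early stoppers who stay in.** Six weeks of treatment plus one week puts the scan at nominal Day 49. For a patient who stops after week k, the gap is 49 − 7k days:

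| Stop after week | 1 | 2 | 3 | 4 | 5 |
|---|---|---|---|---|---|
| Days off drug at scan | 42 | 35 | 28 | 21 | 14 |

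**4. Table 1's labels.** With Baseline as Day 1, Week k starts on Day 7(k − 1) + 1. Visit 7 is then Day 36 and Visit 8 is Day 43, which is 6 weeks after Baseline. The text implies 6 + 1 = 7 weeks. Two readings follow:

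| Reading | Last dose | Gap to Visit 8 | With ±2 days |
|---|---|---|---|
| Five dispensings (Visits 2–6), assumed 7 days each | Day 35 | 43 − 35 = 8 | 6 to 10 |
| A full 42 days of dosing on the same grid | Day 42 | 43 − 42 = 1 | −1 to 3 |

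The first reading agrees with item 6 that the scan is about a week off drug. The second puts the scan next to the last dose and contradicts item 6.

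**5. A scan at Visit 7 instead.** On the first reading the gap is 36 − 35 = 1 day, at most 3 with the window. On the second, Day 36 lies before the last dose. Either way the scan is within 3 days of the last dose or on treatment.

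**The case against.** Several points on the other side carry weight.

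*The timeline is not settled.* Only item 6 ties the visit to the last dose; item 7, Section 7.2.4 and Table 1 name only a visit. Some details suit Visit 8 as an end-of-treatment visit: the column is headed 8/ET, Table 1 marks CGI-S there but not at Visit 7, and Section 7.2.4 schedules a compliance check and return of unused medication. Against that, Table 1 heads the column as safety follow-up, Section 11.3 equates Week 6 with Visit 7, and dispensing ends at Week 5. It stands that the passages conflict. It would be too strong to say that no completer could be scanned on drug under any reading.

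*The 3-day limit was not written for imaging.* A reader might infer that the scan breaks the plan's own rule. It does not: the rule covers efficacy assessments under the primary estimand. It is the only off-treatment definition in the document, so it serves as a benchmark by analogy.

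*Aim 2 does not say the effect must be seen while drug is taken.* A post-treatment scan in both arms gives a legitimate randomised contrast of what remains after a course of treatment. That is correct. But items 4 and 6 speak of mechanism of treatment action, item 5 of drug-induced change, and nowhere is a reason given for scanning off drug.

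*No mediation model is specified.* Mediation appears in item 5 as a possibility, and Section 11.2 contains no such analysis. Table 1 also marks MADRS at Visit 8, although the Section 7.2.4 list omits it, so same-visit symptom data may exist. The order of measurement therefore limits the item 5 claim about the Week 6 outcome; it does not invalidate a planned test.

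*Imaging lies outside the confirmatory hierarchy* of Section 11.4. That stands and limits the severity.

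**Conclusion.** The point holds for the pre-to-post and mechanism part of Aim 2, as a should-fix. As item 6 is written, every completer's second scan falls about 7 days after the last dose (5 to 9 with the assumed window). Early stoppers who stay in are scanned about 14 to 42 days after theirs and, with no timing limit in Section 11.2, are analysed with completers. The conclusion rests on item 6 over the Table 1 reading that puts Visit 8 about one day after the last dose.

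Three stronger conclusions might be inferred, and the protocol supports none of them:

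- That Aim 2 fails as a whole. The predictor part uses the pre-dose scan and is untouched.
- That a true on-drug effect is biased toward zero. This would require the effect simply to fade after stopping. A discontinuation effect could distort the comparison either way, so the direction is unknown.
- That the trial's main result is at risk. MADRS change, response, remission and CGI-S do not depend on the scan.

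**What to change.** 1. Schedule the second fMRI at the end-of-treatment visit (Visit 7) or within 3 days of the last dose. State whether the 8/ET mark in Table 1 means a scan at the early termination visit.
2. Align item 6, item 7, Section 7.2.4, the fMRI row of Table 1 and the imaging payment text in items 34a and 34c, which names Visit 8.
3. Reconcile Table 1's week labels (Baseline = Week 1, Visit 8 = Week 7) with the 6 weeks of treatment plus 1 week of follow-up in items 6 and 7.
4. In Section 11.2, record days since last dose for each scan, take on-treatment scans as the main imaging measure, and describe later scans separately.
5. If the Visit 8 scan is kept, restate this part of Aim 2 as brain change persisting after treatment ends and drop the claim about mechanism of treatment action.

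The cost is a protocol amendment and a longer Visit 7. The number of scans does not change.
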